6.1.6.2 Preparation of Groin product application Area

A skin irritation assessment will be performed by the Investigator or designated sub-investigators trained by the Investigator, using the Skin Irritation Rating Scale (Table 6). If an irritation score of 1 or greater is assigned for any individual skin condition at the Product Application Day baseline, the subject will be excluded from the product application phase of the study for the groin.

The product application site within the groin region (groin product application area) is defined as the inner aspect of the upper thigh within and parallel to the inguinal crease below the groin (APPENDIX 1). Using a 1.3" x 5" (3.3 cm x 12.7 cm) sterile template, the corners of each groin product application area will be marked directly on the skin using a non-toxic skin marker. Four sampling sites will be numbered within each groin product application area, on each side of the groin region. The positioning and numbering of the groin sampling sites are standard for all subjects. Sampling sites on the contra-lateral side of the groin will be numbered in a mirror-image orientation. The four sampling sites within each groin product application area represent one baseline (pre-application) site and three post-application sample sites (30-seconds, 10-minutes, and 6-hours).

After groin product application areas are marked and sample sites numbered, baseline samples will be collected from the appropriate site per the randomization schedule in each product application area using the scrub cup technique (see Section 6.3.1.1 Microbial Sample Collection/ Scrub Cup Technique).

6.1.6.3 Study Product Materials Application

After baseline sample collection is completed, the randomly assigned contra-lateral product application areas will be treated with the assigned study product materials.

The study products will be applied and the sampling configurations will be performed per the randomization schedule and the Study Product Application Instructions (Appendix 5). The duration of application time for each location will be recorded.

The study product material weight will be measured before and after application to the product application site and recorded as described in the Study Product Application Instructions (Appendix 5).

Table 5 contains a summary of the study products, anatomical sites evaluated, application time, dry time and coverage area.

Table 5: Anatomical body sites, application times, dry times and coverage area for each study product.

| Study Product | Body Site | Application Time | Dry Time | Area of Coverage |
|---------------|-----------|------------------|------------|----------------------------------|
| IP | Abdomen | 30 seconds | 30 seconds | 2.5" x 2.5" (6.4 cm x 6.4 cm) |
| | Groin | 2 minutes | 1 minute | 1.3" x 5" (3.3 cm x 12.7 cm) |
| AC | Abdomen | 30 seconds | 30 seconds | 2.5" x 2.5" (6.4 cm x 6.4 cm) |
| | Groin | 2 minutes | 1 minute | 1.3" x 5" (3.3 cm x 12.7 cm) |
| NC | Abdomen | 30 seconds | 30 seconds | 2.5" x 2.5" (6.4 cm x 6.4 cm) |
| | Groin | 2 minutes | 1 minute | 1.3" x 5" (3.3 cm x 12.7 cm) |
| RS | Abdomen | 30 seconds | 30 seconds | 2.5" x 2.5" (6.4 cm x 6.4 cm) |
| | Groin | 2 minutes | 1 minute | 1.3" x 5" (3.3 cm x 12.7 cm) |

6.2 Efficacy Assessments

6.3.1 Post Application Sample Collection and Assessments

The microbial samples will be collected at 30 seconds (± 5 sec.), 10 minutes (± 30 sec.) and 6 hours (± 30 min.) post product application for both the abdomen and the groin regions. Post application timing begins upon completion of the study product application, including drying time. Microbial samples will be collected using the scrub cup technique (see Section 6.3.1.1 Microbial Sample Collection/ Scrub Cup Technique).

After the 10-minute (± 30 sec.) samples have been collected, a sterile non-occlusive dressing will be secured over the remaining sample sites to protect the sites from contamination between sampling times. Subjects will be instructed to ensure the non-occlusive dressing remains intact and dry until the 6 hours sampling occurs.

Prior to collection of the 6-hour sample, the technician will perform an assessment of the 6-hour sample site to determine if the gauze appears dry, clean, and intact. Subjects will also be asked to provide a verbal assessment of the sample site regarding any adjustments to the gauze and if the gauze remained intact and dry from time of placement until the 6 hour evaluation.

A skin irritation assessment will be performed by the Investigator or designated sub-investigators trained by the Investigator prior to collection of each post product application microbial sample collection (30-seconds, 10-minutes and 6-hours) and a corresponding rating score for each individual skin condition will be recorded in the subject's CRF.

If an irritation score of 3 is assigned for any individual skin condition at any post product application observation, the subject will be discontinued from the study and an AE will be recorded.

Following final sample collection at the 6 hour time point or early study discontinuation, the remaining study product will be removed from the subjects' skin using soap and water.

6.3.2 Microbial Sample Collection / Scrub Cup Technique

Quantitative cultures (baselines and post product application) will be obtained by a modification of the cylinder sampling technique of Williamson-Kligman scrub cup technique. To collect the samples, a sterile scrub cup (2.20 cm I.D., skin surface area of 3.80 cm²) will be placed on the site and held firmly to the skin. Sampling solution (SS) (3.0 mL) will be pipetted into the cup and the skin will be scrubbed with moderate pressure for one minute using a sterile rubber policeman. Using a sterile transfer pipette, the SS will be removed and placed in a sterile test tube. An additional 3.0 mL of fresh sampling solution will be pipetted into the cup and the scrub procedure will be repeated. This solution will be pooled with the first solution collected.

6.3.3 Bacterial Enumeration Methods

Following sample collection, 10-fold serial dilutions (1 mL sample + 9 mL PBW) will be prepared using PBW. One-mL aliquots of appropriate dilutions will be pour-plated in triplicate using trypticase soy agar containing neutralizers (TSA+N). Samples must be plated within 30 minutes of collection.

Serial dilutions of collected baseline screening samples as follows:

- for groin sites: 1 serial dilution (10^{-3})
- for abdomen sites: 1 serial dilution (10^{-1})

Serial dilutions of collected treatment day (D0) samples as follows:

for groin sites

- Baseline: 3 serial dilutions (10^{-3} , 10^{-4} and 10^{-5})
- 30 seconds: 6 serial dilutions (10^0 , 10^{-1} , 10^{-2} , 10^{-3} , 10^{-4} and 10^{-5})
- 10 minutes: 6 serial dilutions (10^0 , 10^{-1} , 10^{-2} , 10^{-3} , 10^{-4} and 10^{-5})
- 6 hours: 6 serial dilutions (10^0 , 10^{-1} , 10^{-2} , 10^{-3} , 10^{-4} and 10^{-5})

for abdomen sites

- Baseline: 3 serial dilutions (10^{-1} , 10^{-2} and 10^{-3})
- 30 seconds: 4 serial dilutions (10^0 , 10^{-1} , 10^{-2} and 10^{-3})
- 10 minutes: 4 serial dilutions (10^0 , 10^{-1} , 10^{-2} and 10^{-3})
- 6 hours: 4 serial dilutions (10^0 , 10^{-1} , 10^{-2} and 10^{-3})

After 72 ± 4 hours of aerobic incubation at $30 \pm 2^\circ\text{C}$, colonies will be counted and viable cells in the original sample will be calculated according to Standard Operating Procedures (SOPs). After incubation, plates may be refrigerated up to 48 hours prior to counting.

Raw colony counts from each dilution will be recorded on the appropriate CRFs for each subject. The average number of microorganisms recovered will be calculated using the formula to convert the bacterial counts into \log_{10} CFU/cm² of skin:

$$R = \log_{10} \left[\frac{F \left(\frac{\sum_{i=1}^3 c_i}{n} \right) D}{A} \right]$$

Where: R = the average CFU count in \log_{10} scale per cm² of skin.

F = total mL of sampling solution (SS) added to the sampling cylinder (6 mL);

$\frac{\sum_{i=1}^3 c_i}{n}$ = average of the triplicate colony counts used for each sample collected

D = Dilution factor of the plates counted. One of 10^0 , 10^1 , 10^2 , 10^3 , 10^4 , or 10^5 .

A = Inside area of the sampling cylinder (3.80cm²)

The average CFU/mL, CFU/cm², and \log_{10} CFU/cm² will be calculated for samples from each product application site in the same manner.

In order to avoid potential calculation problems due to taking the logarithm of zero, values of less than 1 CFU/cm² will be treated as 1 CFU/cm², such that the \log_{10} transformation is not less than zero.

6.3 Safety Assessments

The principal measures of safety will be skin reactions using the modified Berger Bowman irritation assessment scale and the incidence of AEs reported during the study

6.3.1 Adverse Events

The incidence of adverse events reported during this study will be collected for assessment of safety. Details on the AE management, reporting and assessment can be found in Section 9.

6.3.2 Skin Irritation Score

Subjects that receive study products will be monitored for skin irritation using the modified Berger Bowman irritation assessment scale. Skin irritation assessment will be performed as outlines in Section 6.2 Study Visits.

If a reaction occurs on the skin test site, it may be needed to take photographs of the skin test site only. These photographs will be shared with the Principal Investigator / Sub-Investigator, the sponsor and the study staff only and will be used for the Principal Investigator / Sub-Investigator's review and assessment of the reactions.

Table 6: Modified Berger Bowman Skin Irritation Rating Scale

| Skin Irritation Rating Scale | | |
|--|----------------|--------------------------------|
| Reactive area(s) within the product application site only | | |
| Condition | Rating | Description |
| Erythema | 0 | No reaction |
| | 1 | Mild and/or transient redness |
| | 2 ^a | Moderate redness |
| | 3 ^b | Severe redness |
| Edema | 0 | No reaction |
| | 1 | Mild and/or transient swelling |
| | 2 ^a | Moderate swelling |
| | 3 ^b | Severe swelling |
| Rash | 0 | No reaction |
| | 1 | Mild and/or transient rash |
| | 2 ^a | Moderate rash |
| | 3 ^b | Severe rash |
| Dryness | 0 | No reaction |
| | 1 | Mild and/or transient dryness |
| | 2 ^a | Moderate dryness |
| | 3 ^b | Severe dryness |

^a = Represents significant irritation in any category and may require subject’s removal from the study.

^b = A rating of 3 on the skin irritation scale in any category will be recorded as AE and will require subject’s removal from the study.

7.0 INTERRUPTION OR DISCONTINUATION OF PARTICIPATION

7.1 Discontinuation of study subjects

Subjects may request withdrawal from the study at any time or may be withdrawn at the discretion of the Investigator for any of the following reasons:

- Adverse Event/Concurrent Illness
- Noncompliance with study requirements or restrictions
- Failure to meet ongoing inclusion criteria, or development of an excluding condition
- Protocol deviation
- Withdrawal of consent
- Subject is lost to follow up
- Administrative issues
- Any other reason which, in the opinion of the Investigator, makes the subject's participation in the study not in his or her best interest.

If a subject withdraws from the study, all efforts will be made to complete a final evaluation, if possible.

7.2 Discontinuation of specimen analysis.

Discontinued subjects will not be replaced. If needed, additional subjects will be enrolled with a sequential, unique randomization code according to the randomization schedule.

No data will be collected from subjects after the point of discontinuation except as needed to follow ongoing AEs. All study data collected from the subject up to the point of discontinuation will be recorded on the CRF, entered into the study database, and included in subsequent analyses, as appropriate.

7.3 Discontinuation Visits and Follow-up Procedures

For subjects discontinued due to AEs, the clinical course of the event will be followed according to the procedures outlined in section 9.2.1 Follow-up of Adverse Events.

8.0 RISK / BENEFIT ASSESSMENT

8.1 Potential Risks

Subjects participating in this study could experience side effects to the skin (from either the Investigational or Comparator products and/or study procedures) such as:

- skin reactions, primarily confined to the area of application
- local minimal or moderate erythema
- minimal edema
- application site pruritus
- rash
- papules
- vesicles
- burning sensation
- allergic reaction including in rare cases anaphylaxis

Subjects may also experience folliculitis from clipping.

There may be risks from participating in this study that are unknown.

8.2 Potential Benefits

There are no direct benefits to the subject for participation in this study. The findings may reveal information that will allow for a better understanding of the antimicrobial effectiveness of a single Swabstick impregnated with 1.75mL of 2% (w/v) chlorhexidine gluconate (CHG) in 70% (v/v) isopropyl alcohol.

9.0 SAFETY

9.1 Adverse Event Definitions

Adverse Event (AE):

Any untoward medical occurrence in a patient or clinical investigation subject administered an investigational product (drug or device), which does not necessarily have to have a causal relationship with the treatment.

An adverse Event (AE) can therefore be any unfavorable and unintended sign (including an abnormal laboratory finding, for example), symptom, or disease temporally associated with the use of an investigational product, whether or not considered related to the investigational product.

Note 1: This definition includes events related to the investigational product or the comparator.

Note 2: This definition includes events related to the procedures involved

Serious Adverse Event (SAE):

A serious adverse event is an event that in the view of either the Investigator or Sponsor, results in any of the following outcomes:

- Death
- life-threatening illness or injury
- permanent impairment of a body structure or body function
- in-patient hospitalization or prolongation of hospitalization
- injury, significant disability Fetal distress, fetal death, or a congenital abnormality or birth defect
- Other important medical event, that requires medical or surgical intervention to prevent any of the above

Note 1: “Planned hospitalization for pre-existing condition, or a procedure required by the protocol, without serious deterioration in health, is not considered a serious adverse event”.

Note 2: “Medical and scientific judgement should be exercised in deciding whether expedited reporting is appropriate in other situations, such as important medical events that may not be immediately life-threatening or result in death or hospitalization but may jeopardize the patient or may require intervention to prevent one of the other outcomes listed in the definition above. These should also usually be considered serious. Examples of such events are intensive treatment in an emergency room or at home for allergic bronchospasm; blood dyscrasias or convulsions that do not result in hospitalization; or development of drug dependency or drug abuse”.

9.2 Adverse Event (AE) Management

Collection of adverse events will begin after the subject has signed the Informed Consent form through the end of study conduct.

At each study contact, the subject will be questioned in an open-ended manner regarding any new or worsening undesirable signs or symptoms they may have experienced since the previous contact. Signs and symptoms must be comprehensively documented on the appropriate source documentation. All related signs and symptoms should be grouped under one diagnosis if possible.

Each sign, symptom, disease or illness reported must be evaluated by the Investigator or designee to determine if it meets the definition of an AE.

Any irritation of the application sites that results in the withdrawal of the subject from the study or, in the opinion of the Investigator or designate, warrants medical attention or medication will be considered AEs that will be subjected to the same criteria as all other AEs.

If an AE or SAE reaction occurs on the skin test site, it may be needed to take photographs of the skin test site only. These photographs will be shared with the Principal Investigator / Sub-Investigator, the sponsor and the study staff only and will be used for the Principal Investigator / Sub-Investigator’s review and assessment of the reactions.

9.2.1 Follow-up of Adverse Events (AEs)

Adverse events that are present after the completion of the subject’s scheduled study visit will be followed up to 14 days by means of the investigational site contacting the subject via telephone or by any other means considered appropriate. If the subject’s adverse event is still ongoing past the 14 days, the Investigator will communicate with the sponsor Medical Monitor (via telephone and/or email) as to the need for further follow-up. In the case of discrepancies, the Investigator’s judgement will prevail. All communications with the subject and medical monitor will be documented appropriately.

Adverse Events whose onset occurs up to 14 days after the end of the subject’s study participation, will be recorded and will require the Investigator to communicate with the sponsor Medical Monitor as to the need for further follow-up as described above. All contacts will be documented appropriately.

The clinical course of any serious adverse event will be followed according to accepted standards of medical practice until the event resolves, stabilizes, or in the opinion of the Investigator, is no longer considered clinically significant as it relates to the study product and/or study procedures.

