9.4.2 Pregnancies

Investigators must instruct subjects to inform them immediately if they become pregnant during the trial.

In case of a pregnancy during the participation in the trial, the subject will be immediately considered for premature discontinuation.

The pregnancy will be registered on the CRF/eCRF protocol deviation form. In addition, the Pregnancy Form (which is independent of the CRF/eCRF) will be completed and entered into the EDC with all the available information within the same time frame and following the same routing as for a SAE, described previously. The Investigator will make every effort to obtain all information related to the pregnancy and its final outcome, which may involve follow-up after the trial has ended. Pregnancies will be followed up for maximally 4 weeks after delivery or termination of the pregnancy.

All pregnancies discovered by the Investigator after the termination of the trial but which were initiated during the participation in the trial will be reported to BD (see details above) as occurring during the trial.

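### Protocol 7.2 bars recording of new adverse events after discontinuation, while 9.2.1 requires it for 14 days after participation ends; the two need reconciling

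*Protocol*

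**What the plan says.** Four places in the protocol bear on what is recorded after a subject leaves.

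- **Section 7.2:** "No data will be collected from subjects after the point of discontinuation except as needed to follow ongoing AEs". It adds that "All study data collected from the subject up to the point of discontinuation will be recorded on the CRF" and used in analyses as appropriate.
- **Section 7.3:** "For subjects discontinued due to AEs, the clinical course of the event will be followed" under 9.2.1. It does not mention new events, or subjects discontinued for other reasons.
- **Section 9.2.1:** "Adverse Events whose onset occurs up to 14 days after the end of the" subject's participation must be recorded. Discontinued subjects are not exempted.
- **Section 9.4.2:** a subject who becomes pregnant is considered for premature discontinuation, and yet "Pregnancies will be followed up for maximally 4 weeks after delivery or termination of the pregnancy".

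Section 9.2 sets the general collection period: "Collection of adverse events will begin after the subject has signed the Informed Consent form through the end of study conduct". The incidence of AEs is one of the two named safety endpoints (Protocol 3.1.2, SAP 2.4). SAP 6.2.3 lists AEs for all enrolled subjects (Listing B.6) and tabulates subjects with an AE in the ITT set, by product and overall (Table A.4.2). It has no rule for AEs that start after discontinuation.

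**The concern.** A reaction that begins after discontinuation is not an ongoing AE. Section 7.2 therefore excludes it, while 9.2.1 requires it if it begins within 14 days of the end of participation. Staff who follow one section break the other.

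This matters because discontinuation can be tied to the safety outcome. An irritation score of 3 requires removal from the study (Protocol 6.2 and Table 6), and a score of 2 may lead to it. Each subject also carries two different products, one on each side of the body. A subject removed for a reaction to one product can later react at the other product's site, and that second event bears on the safety profile of the other product. If 7.2 governs, the event need not reach the case report form, and so reaches neither the listing nor the table.

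**Working it through.** The plan states no figure to reproduce. The check is a comparison of texts, then a trace of each case through the SAP outputs.

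**1. Do the rules cover the same subjects?** Section 9.2.1 speaks of the end of participation and 7.2 of discontinuation. Discontinuation ends participation, and 9.2.1 makes no exception, so both apply to a discontinued subject.

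**2. Is 7.2 about specimens only?** Its heading refers to specimen analysis. But the sentence covers all data, and its single exception concerns AEs, so it cannot be confined to specimens.

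**3. Does 7.3 bridge the gap?** Only in part: "the clinical course of the event will be followed according to the procedures outlined in section 9.2.1". That carries forward the event that caused discontinuation. It leaves out new events and subjects discontinued for any other reason.

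**4. What is lost if 7.2 is applied as written?** All cases below are treated subjects with a new event inside the 14-day period.

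| Case | Listing B.6 | Product column, Table A.4.2 | Overall column, Table A.4.2 |
|---|---|---|---|
| Removed for irritation; later reaction at the other product's site | event missing | other product one subject short, if AEs are attributed by treated site | unchanged, already *Yes* |
| Removed for irritation; later reaction at the same product's site | event missing | unchanged | unchanged |
| Discontinued for a non-AE reason, no earlier AE; later rash | event missing | one subject short | one subject short |
| Completer; later rash | recorded under 9.2.1 | counted | counted |

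The irritation rows follow because 9.2 makes any irritation that leads to withdrawal an AE, whatever its score. The overall column counts unique subjects. The SAP does not say how AEs are assigned to product columns, so the effect in the first row rests on attribution by site.

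**5. How much does one missed subject matter?** The protocol's block table gives the minimum number of evaluable subjects per product over 4 blocks.

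- Each product other than the reference standard: 4 × (16 + 27 + 27) = 280. One subject is 1/280 = 0.36 percentage points.
- Reference standard: 4 × (16 + 16 + 16) = 192. One subject is 1/192 = 0.52 points.
- Overall: 4 × 129 = 516. One subject is 1/516 = 0.19 points.

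The ITT set should be at least this large, so these are upper limits per missed subject. The number of such subjects cannot be derived, because the documents give neither a discontinuation rate nor an AE rate.

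**6. Pregnancy.** Follow-up to 4 weeks after delivery is not the following of an ongoing AE, so read literally 7.2 excludes it too. This does not affect the AE endpoint, but the same sentence in 7.2 is the cause.

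**The case against.** The best case on the other side is that Section 9 plainly means to operate after discontinuation. Besides 9.2.1, AE collection runs to the end of study conduct (9.2), all AEs go into the case report form (9.3), every serious AE goes to the sponsor within 24 hours (9.4), and pregnancy follow-up must outlast discontinuation to make sense. This is good evidence of intent, and the revision history suggests an oversight: version 2.0 added 9.2.1 and revised 7.1 and 7.3, and lists no change to 7.2. But no sentence gives Section 9 precedence, and 7.2 deals with AEs expressly.

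A reader might infer more than the documents support, in three ways.

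- **That AE incidence is understated where risk is highest.** Subjects removed for irritation already have an AE and already count as *Yes* overall, so a second event cannot change that figure. If their event is ongoing, the site contacts them for up to 14 days, and 9.2 has them asked about new symptoms at each contact. A completer without an AE has no scheduled contact after the 6-hour visit. What remains is that hearing of a new event is not the same as being allowed to record it.
- **That discontinued subjects have a window of 0 days against 14 for completers.** This holds only if 7.2 overrides Section 9, which is the unsettled question.
- **That sites will diverge.** There is one site. The risk is uneven handling between staff and subjects.

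Two further objections stand. The group is narrow: for the ITT summary, only discontinuation between application and the 6-hour sample on the same day counts. And since 7.1 lists withdrawn consent and loss to follow-up among the reasons for discontinuation, recording exactly as for completers cannot be promised for everyone.

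**Conclusion.** The contradiction is real and unresolved in either document. If 7.2 is applied as written, a new AE in a treated subject who discontinued can be left out of the listing and of the by-product counts. It can be left out of the overall count only when the subject left for a reason other than an AE and had no AE before. The number affected cannot be computed and is probably small, given the short period on one day in which a treated subject can discontinue.

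This rests on discontinuation ending participation in the sense of 9.2.1 and, for the by-product effect in subjects who already have an AE, on AEs being attributed to the treated site. AE incidence is descriptive only, so efficacy conclusions, alpha and sample size are untouched. The point is worth correcting because it concerns a named safety endpoint and is cheap to settle. It does not show that AE incidence will be understated.

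**What to change.** Reconcile 7.2, 7.3, 9.2.1 and 9.4.2 of the protocol.

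- In 7.2, state that efficacy data collection stops at discontinuation, but that AEs (ongoing, or new within the period of 9.2.1), serious AEs and pregnancies continue to be recorded under Section 9, as far as the subject's remaining consent and contactability allow.
- In 7.3, refer all discontinued subjects to 9.2.1 for AE recording, not only those discontinued due to an AE.
- A sentence in SAP 6.2.3 on how AEs starting after discontinuation are counted and assigned to product columns would complete the repair.

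The cost is a few sentences, with the ethics committee submission that Protocol 15.4 requires, and a check that the consent form agrees. No new visit or procedure is needed, because 9.2.1 already provides for recording these events. The change concerns data recording only, not clinical care.
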